## 4 Statistical methods: Analysis sets

The **safety analysis set** will include all participants that received any study drug.

The **PK analysis set** will include all participants with at least one available valid (i.e., not flagged for exclusion) PK concentration measurement, who received any study drug and with no protocol deviations that impact on PK data.

The **efficacy/PD analysis set** will include all participants with available efficacy/PD data and no protocol deviations with relevant impact on efficacy/PD data.

For all analysis sets, participants will be analyzed according to the study treatment(s) received.

Throughout this document, 'treatment' refers to the treatment arm of a cohort that each participant is assigned to.

For treatments with an extended half-life, EOS1 will be required as a standard, non-EOS post-treatment follow up visit, and EOS2 will serve as the EOS visit. For all other treatments, EOS1 will serve as the EOS visit. If a participant discontinues study treatment early, the participant should be scheduled for a subsequent visit at which time all assessments at the EOS1 visit should be performed. For treatments with an extended half-life, if a participant discontinues

early after EOS1, then the participant should be scheduled for a subsequent visit at which time all assessments at the EOS2 visit should be performed.

The Day 113 (EOS1) visit for treatments with no extended half-lives and the Day 141 (EOS2) visit for treatments with extended half-lives will be pooled and reported/analyzed together under a common EOS visit, labeled as 'EOS', in the reporting/analysis. The Day 113 (EOS1) visit for treatments with extended half-lives will be reported/analyzed as a distinct visit, labeled as 'Day 113', in the reporting/analysis.

For the End of Study (EOS) visit, only data from study completers will be included in the efficacy summary/analysis tables/figures. Safety summary/analysis tables/figures will include data from all participants, i.e., both study completers and non-study completers for the End of Study (EOS) visit.

## 4.1 Cohort-specific information:

### 4.1.1 Cohort 1:

Cohort 1 will evaluate the use of LYS006 alone and tropifexor (LJN452) in combination with LYS006 for the treatment of elevated liver fat, liver inflammation and liver fibrosis in NAFLD participants who manifest a NASH-like biomarker phenotype. The drug combination of LYS006 and tropifexor (LJN452) may provide clinical benefit beyond that of either drug alone, considering different, complementary mechanisms of action of these drugs.

Approximately 50 participants will be randomized in a 1:1 ratio to one of the following treatment arms:

- Treatment arm 1: LYS006 Commercially Confidential Information
- Treatment arm 2: Tropifexor (LJN452) Commercially Confidential Information + LYS006 Commercially Confidential Information

The treatments used in cohort 1 (i.e. LYS006 and Tropifexor) do not have extended half-lives, so the EOS1 visit will serve as the end-of-study visit for participants randomized to any of the two treatment arms of cohort 1 (i.e. for all cohort 1 participants).

### 4.1.2 Protocol deviation codes

The analysis sets and protocol deviation codes are related as follows:

**Table 4-1 Protocol deviation codes and analysis sets**

Category Deviation code	Text description of deviation	Data exclusion
Participants are excluded from safety analysis in case of these PDs:		Exclude participant from safety analysis set
INCL01	Written informed consent must be obtained prior to screen procedures	

Category Deviation code	Text description of deviation	Data exclusion
Participants are excluded from PK analysis in case of these PDs:		Exclude participant from PK analysis set
INCL01	Written informed consent must be obtained prior to screen procedures	
OTH13	Additional data collected is not as per effective ICF/Protocol requirement	Exclude only the PK data that the protocol deviation relates to from the visit the protocol deviation occurred on
Participants are excluded from efficacy/PD analysis in case of these PDs:		Exclude participant from efficacy/PD analysis set
INCL01	Written informed consent must be obtained prior to screen procedures	
OTH12	Follow up end of study MRI was not completed within 7 days of treatment discontinuation	Exclude participant from imaging data analyses from the visit the protocol deviation occurred on (for imaging data, visit can be either Day 85 or EOS)
OTH13	Additional data collected is not as per effective ICF/Protocol requirement	Exclude only the efficacy/PD data that the protocol deviation relates to from the visit the protocol deviation occurred on
COMD01	Following randomization initiation of new antidiabetic, insulin, betablockers, thiazide diuretics, fibrates, statins, niacin, ezetimibe, thyroid hormone, psychotropic, estrogen, birth control	Exclude participant from all efficacy/PD analyses from the protocol deviation's study day (i.e., prohibited medication's start day) onwards

Category Deviation code	Text description of deviation	Data exclusion
TRT03	Treatment modification guidelines per protocol not followed	Exclude participant from all efficacy/PD analyses from the protocol deviation's study day onwards – PD is exclusionary only under specific criteria*

\**TRT03 PD is exclusionary if dose interruption is > 2 days and/or decreased dose is continued for > 2 weeks.*

If updates to this table are needed, an amendment to the SAP needs to be implemented prior to DBL.

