## **9.2 Withdrawal of informed consent/Opposition to use data/biological samples**

Withdrawal of consent/opposition to use data/biological samples occurs when a participant:

- Explicitly requests to stop use of their biological samples and/or data (opposition to use participant's data and biological samples), and
- No longer wishes to receive study treatment, and
- Does not want any further visits or assessments (including further study-related contacts)

In this situation, the investigator should make a reasonable effort (e.g., telephone, e-mail, letter) to understand the primary reason for the participant's decision to withdraw his/her consent/opposition to use data/biological samples and record this information.

Where consent to the use of Personal and Coded Data is not required in a certain country's legal framework, the participant therefore cannot withdraw consent. However, they still retain the right to object to the further collection or use of their Personal Data.

Study treatment must be discontinued and no further assessments conducted, and the data that would have been collected at subsequent visits will be considered missing.

Further attempts to contact the participant are not allowed unless safety findings require communicating or follow-up.

If the participant agrees, a final evaluation at the time of the participant's withdrawal of consent/opposition to use data/biological samples should be made as detailed in the [Assessment schedule](#) (please also refer to [Section 8](#)).

Novartis will continue to retain and use all research results (data) that have already been collected for the study evaluation, including processing of biological samples that has already started at the time of consent withdrawal/opposition. No new Personal Data (including biological samples) will be collected following withdrawal of consent/opposition.

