### **12.1 Analysis sets**

The safety analysis set will include all participants that received any study drug.

The PK analysis set will include all participants with at least one available valid (i.e., not flagged for exclusion) PK concentration measurement, who received any study drug and with no protocol deviations that impact on PK data.

The efficacy/PD analysis set will include all participants with available efficacy/PD data and no protocol deviations with relevant impact on efficacy/PD data.

For all analysis sets, participants will be analyzed according to the study treatment(s) received.

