## **8 Statistical methods for safety and tolerability data**

The primary objective of this study is to determine the safety and tolerability of single or combination therapy during 12 weeks of treatment.

All participants within the safety analysis set will be included in the safety data analysis.

For participants with protocol deviations affecting the safety analyses, the data will be excluded as described in [Table 4-1](#) above.

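### SAP Table 4-1 removes dosed participants from the safety set for any INCL01 consent deviation, including those who signed late but before dosing, although both documents define the set as everyone dosed

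*SAP*

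**What the plan says.** Protocol 12.1 defines the set without qualification: "The safety analysis set will include all participants that received any study drug". SAP 4 repeats that the safety set "will include all participants that received any study drug". The PK set in the same SAP section is conditional; it takes participants "who received any study drug and with no protocol deviations that impact on PK data". The efficacy/PD set carries a similar deviation clause. The safety set has none.

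SAP 4.1.2, Table 4-1, opens with a safety block holding a single code, INCL01, described as "Written informed consent must be obtained prior to screen procedures". The action is "Exclude participant from safety analysis set".

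SAP 8 first states "All participants within the safety analysis set will be included in the safety data analysis" and then adds "For participants with protocol deviations affecting the safety analyses, the data will be excluded as described in" Table 4-1.

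Under Protocol 12.4.1 the safety data are the primary endpoints. Protocol 12.4.2 and SAP 8.3 make their analysis descriptive.

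**The concern.** A dosed participant with INCL01 is inside the safety set by definition and outside it by Table 4-1. The two rules give different denominators and can give different event counts.

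The INCL01 label describes timing: consent had to come before screening procedures. It does not separate two quite different people. One signed after a screening procedure but before the first dose. The other never gave valid consent. For the second, excluding the data may be defensible. For the first, the fault concerns what was collected before the signature, yet the rule discards the whole treatment and follow-up record.

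Because the primary analysis is descriptive, its tables are the primary result. With about 25 participants per arm, one person's adverse events can decide whether an event appears in an arm's table at all.

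**Working it through.** **Step 1: compare the rules for one case.** Take a participant who signed after a screening procedure but before Day 1, and then took study drug.

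- Protocol 12.1 and SAP 4: in the safety set, because dosed.
- SAP Table 4-1: INCL01 applies as worded, so out of the safety set.
- SAP 8: Table 4-1 governs the data, so out of the primary safety tables.

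**Step 2: ask which of that person's data the deviation touches.** Protocol 10.1.1 counts an adverse event only once written consent has been given. The treatment-emergent definition in Protocol 12.4.2 and SAP 8.2 rests on onset after first dose, or on worsening, a change in suspected causality or progression to an SAE. For this participant, every recorded adverse event therefore follows consent. Only measurements taken before the signature are affected.

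**Step 3: look for a narrower rule in the same table.** OTH13 (data collected outside the effective consent form or protocol) appears in the PK and efficacy/PD blocks. It removes only the data concerned, at the visit concerned. The SAP thus already has a data-level exclusion for a consent-related deviation.

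**Step 4: size.** Neither document gives an INCL01 count or a planned safety precision, so there is no stated figure to reproduce.

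Inputs:
- Arm size n = 25 (Protocol 5: about 25 enrolled per arm; Protocol 17.1: about 50 randomised 1:1).
- Dosed participants excluded per arm, m: assumed, 1 to 3.
- Participants with a given event, k; of these, j are among those excluded.

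Crude incidence moves from k/n to (k − j)/(n − m).

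| Events k | Before | m = 1, excluded person had the event | m = 1, excluded person did not |
|---|---|---|---|
| 1 | 1/25 = 4.0% | 0/24 = 0% | 1/24 = 4.2% |
| 2 | 2/25 = 8.0% | 1/24 = 4.2% | 2/24 = 8.3% |
| 3 | 3/25 = 12.0% | 2/24 = 8.3% | 3/24 = 12.5% |

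If m = 2 and both had the event, 3/25 (12.0%) becomes 1/23 (4.3%).

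The loss of detection from the smaller denominator alone is small. The chance of seeing at least one case of an event with a true rate of 5% (an illustrative rate) is 1 − 0.95^(n − m):

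- 25 in the set: 72.3%
- 24: 70.8%
- 23: 69.3%
- 22: 67.6%

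What matters is whether an excluded person had an event, far more than the reduced n.

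**The case against.** **The SAP can be read as coherent.** Section 4 gives a general definition, Table 4-1 lists one exception, and Section 8 applies it. This largely stands: a programmer following the SAP would exclude the participant. It does not remove the departure from Protocol 12.1, and the exception is missing from the SAP's own definition.

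**Exclusion may be legally required.** Where valid consent was never obtained, that is a fair defence. The documents do not show how INCL01 is assigned, so it may in practice be kept for such cases. The label, however, does not say so, and as worded it also covers late signers.

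**The case should be rare.** Protocol 5 bars enrolment on breach of any entry criterion, and Protocol 11.3 requires full verification that consent is present. Both lower the likelihood, but the table row exists for the cases that get through.

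**Stronger readings that the documents do not support:**

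- A reader might infer that a serious event could escape safety oversight. It could not by this route: SAE reporting (Protocol 10.1.3), the arm stopping rules (9.2.1) and Safety Assessment Committee review (10.2.1) do not depend on the analysis set.
- A reader might infer a conflict with Protocol 9.2, under which "Novartis will continue to retain and use all research results (data) that have already been collected". That section concerns consent given and later withdrawn. It sets no policy for data collected before consent.
- A reader might infer an undeclared departure from the protocol. The start of SAP 11 is redacted, so this cannot be known.
- A reader might take 1/25 becoming 0/24 as the expected effect. It is the extreme case: it needs a dosed INCL01 participant who also had the arm's only event.

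**Conclusion.** The inconsistency is real and bears on the population for the only primary objective. Protocol 12.1 and SAP 4 keep everyone dosed; Table 4-1, through SAP 8, removes anyone with INCL01. The part that cannot be justified from the documents is the removal of participants who signed late but before dosing, because their adverse event data all follow consent.

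The size depends on an unknown count. With one such participant among 25, an arm's single event either vanishes from the table (4.0% to 0%) or moves from 4.0% to 4.2%. With no such participant, nothing changes. The effect is confined to reported summaries. Whole-participant exclusion where valid consent was never obtained is a separate matter and may be proper.

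**What to change.** Amend the safety block of SAP Table 4-1 before database lock:

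1. Split INCL01 into late consent and consent never validly obtained.
2. Keep in the safety set every dosed participant who gave valid written consent before first dose. Exclude only data collected before the signature, on the OTH13 pattern.
3. Limit whole-participant exclusion to cases where valid consent was never obtained and the data may not be used.
4. State that exception in the safety set definition in both SAP 4 and Protocol 12.1.
5. Report the number of dosed participants excluded, by arm, and list their adverse events separately where permitted.

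The amendment should also say how someone who signed only after the first dose is handled, since that case falls between items 2 and 3. The PK and efficacy/PD blocks list INCL01 too, but those definitions already carry a deviation clause, so this point does not require changing them.

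The cost is a short SAP amendment, which the note under Table 4-1 already provides for, a one-sentence change to Protocol 12.1, and one added count and listing. Design, sample size and conduct are unchanged.

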**Table 6-2 Prohibited medication**

Medication	Prohibition period start	Prohibition period end
Other investigational drugs	Within 5 half-lives of randomization, or within 3 months, whichever is longer; or longer if required by local regulations	End-of-study visit
Obeticholic acid	Within 1 month of randomization	End-of-study visit
Anti-diabetic medications, insulin, beta-blockers, thiazide diuretics, fibrates, statins, niacin, ezetimibe, thyroid hormone, psychotropic medications, estrogen or estrogen containing birth control †	Randomization	End-of-study visit
Vitamin E at doses > 200 IU/day and ≤ 800 IU/day #	Randomization	End-of-study visit
Vitamin E at doses > 800 IU/day	Randomization	End-of-study visit
Pharmacologically-active weight loss medications (for example; lorcaserin, phentermine/topiramate, bupropion-naltrexone HCl, orlistat)	Within 1 month of randomization	End-of-study visit
Strong inhibitors of CYP3A4/5 (for example; boceprevir, clarithromycin, conivaptan, grapefruit juice, indinavir, itraconazole, ketoconazole,	Within 5 half-lives or 7 days of randomization, whichever is longer	End-of-study visit

Medication	Prohibition period start	Prohibition period end
lopinavir, fazodone, nelfinavir, posaconazole, ritonavir, saquinavir, telaprevir, telithromycin, and voriconazole)		
Strong CYP3A inducers (for example; avasimibe, carbamazepine, phenytoin, rifampin, St. John's wort)	Within 5 half-lives or 7 days of randomization, whichever is longer	End-of-study visit

†These medications are prohibited UNLESS the participant has been on stable dosing for at least 3 months prior to randomization. New initiations of these medications during the study are prohibited.

‡This medication is prohibited UNLESS the participant has been on stable dosing for at least 6 months prior to randomization. New initiations of this medication during the study are prohibited.

Please refer to the respective cohort-specific information ([Section 17](#)) prohibited medication section for additional restrictions, as applicable.

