## **9 Discontinuation and completion**

### **9.1 Discontinuation from study treatment and from study**

#### **9.1.1 Discontinuation from study treatment in individual participants**

Discontinuation of study treatment for a participant occurs when study treatment is permanently stopped for any reason (prior to the planned completion of study drug administration) and can be decided by either the participant or the investigator.

Study treatment must be discontinued under the following circumstances:

1. Participant decision
2. Pregnancy
3. Use of prohibited treatment(s)
4. Any situation in which study participation might result in a safety risk to the participant
5. The investigator believes that continuation would negatively impact the safety of the participant or the risk/benefit ratio of trial participation

6. Hypersensitivity (CTCAE Grade 2 or higher) reaction to study medication
7. An adverse event that is CTCAE Grade 4 or higher, regardless of whether the event is suspected to be related to study drug(s)
8. An adverse event that is CTCAE Grade 3 and suspected to be related to study drug(s) (apart from liver and renal events - see below)
  - If a liver or renal event occurs, follow guidelines outlined in [Section 16.1](#) and [Section 16.2](#), respectively, regarding discontinuation of study treatment
9. Any laboratory abnormalities that in the judgment of the investigator, taking into consideration the participant's overall status, prevents the participant from continuing participation in the study

If discontinuation of study treatment occurs, the investigator should make a reasonable effort to understand the primary reason for the participant's premature discontinuation of study treatment and record this information.

Participants who discontinue from study treatment agree to return for the end of treatment assessments (i.e., EOS1 or EOS2) indicated in the Assessment schedule ([Table 8-1](#); and refer to [Section 8](#)).

If the participant cannot or is unwilling to attend any visit(s), the study staff should maintain regular telephone contact with the participant, or with a person pre-designated by the participant. This telephone contact should preferably be done according to the study visit schedule.

After discontinuation from study treatment, at a minimum, in abbreviated visits, the following data should be collected at visits or via telephone/email contact:

- new / concomitant treatments
- adverse events/Serious Adverse Events

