## 6 Statistical methods for Efficacy/Pharmacodynamic (PD) parameters

All participants within the efficacy/PD analysis set will be included in the efficacy/PD data analysis.

Data will be excluded from the efficacy/PD analyses in the following cases:

- For participants with protocol deviations affecting the efficacy/PD analyses, the data will be excluded as described in [Table 4-1](#) above.
- For participants that discontinued treatment early, the following *programming rule* will be applied: *Any efficacy assessments that occurred on or after the treatment discontinuation study day, will be excluded from all efficacy/PD data analyses. An exception to this is the Day 85 visit or EOS visit imaging data (MRI and MRE assessments), that will be excluded only if they occurred prior to study day 56 (i.e., imaging assessments that occurred on or after study day 56, will not be excluded from the imaging analyses).*
- Participants with <80% treatment compliance

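### SAP Table 4-1 has no start-day exclusion for prohibited obeticholic acid, weight-loss drugs, vitamin E or other investigational drugs, so some efficacy values after their use can stay in the analysis

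*SAP*

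**What the plan says.** **SAP Table 4-1.** COMD01 is the only code for concomitant medication. It covers "Following randomization initiation of new antidiabetic, insulin, betablockers, thiazide diuretics" and continues with "fibrates, statins, niacin, ezetimibe, thyroid hormone, psychotropic, estrogen, birth control". The consequence is: "Exclude participant from all efficacy/PD analyses from the protocol deviation's study day (i.e., prohibited medication's start day) onwards". Imaging is not exempted.

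**Protocol Table 6-2.** The COMD01 classes correspond to one row of this table, the drugs allowed only after three months of stable dosing. Separate rows prohibit "Obeticholic acid", "Pharmacologically-active weight loss medications", vitamin E (two dose rows) and other investigational drugs, all to the end-of-study visit. Vitamin E above 200 and up to 800 IU/day is allowed if stable for six months; above 800 IU/day it is not allowed at all.

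**Protocol 9.1.1.** Item 3 requires study treatment to be discontinued when any prohibited treatment is used.

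**SAP section 6.** For early treatment discontinuation, the data dropped are "Any efficacy assessments that occurred on or after the treatment discontinuation study day" or later. MRI and MRE are an exception and are dropped only if done before study day 56. Code OTH12 in Table 4-1 adds that the scan must fall within 7 days of discontinuation.

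**SAP section 4.** The efficacy/PD set leaves out participants whose deviations have a relevant impact on those data. For the EOS visit, efficacy outputs use study completers only.

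**The concern.** The protocol treats both groups of drugs alike: use is prohibited and study treatment must stop. The SAP treats them differently. A newly started beta-blocker removes every efficacy value from its start day. Newly started obeticholic acid does not, and is dealt with only through the discontinuation rule.

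The documents themselves tie some of the uncoded drugs to the endpoints. Protocol 17.1.2.2.3 and the text under Figure 17-2 describe obeticholic acid as an FXR agonist that reduced ALT; tropifexor in Arm 2 is also an FXR agonist. Body weight is a secondary endpoint, and SAP section 7 provides for exploring liver-fat and ALT reduction against weight loss.

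At stake are a few ALT, ELF or liver-fat values that reflect a non-study drug. Protocol 4.3 intends single-drug effects to be compared with historical placebo effects as well as with the combination, so contamination within an arm matters.

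**Working it through.** **Step 1. Match the tables.** Protocol Table 6-2 has 8 medication rows. COMD01 covers 1. The 7 without a code are other investigational drugs, obeticholic acid, two vitamin E rows, weight-loss drugs, strong CYP3A4/5 inhibitors and strong CYP3A inducers. This point concerns the first five of those seven.

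**Step 2. Trace the data after a prohibited start.**

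| Situation | COMD01 drug | Uncoded drug |
|---|---|---|
| Use found, treatment stopped: ALT, ELF and other non-imaging data from the stop day | removed | removed (SAP 6) |
| Same case: non-imaging data between drug start and stop | removed | kept |
| Same case: MRI on or after study day 56, within 7 days of stopping | removed | kept |
| Use found only after treatment is complete: Day 85 values | removed | kept |
| Drug started after treatment is complete: completer's EOS values | removed | kept |

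The imaging row is the clearest. Suppose a drug is started just after the Day 57 visit, found at the Day 71 telephone visit, and treatment is stopped that day. A scan by Day 78 (71 + 7) meets OTH12 and is past study day 56, so it stays. COMD01 would have removed it.

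The second row is narrower than it looks. Medication is to be reviewed at every visit (Table 8-1, footnote 29). If use is found and treatment stopped on a visit day, that visit's laboratory values are already excluded. Values stay only if a visit missed the use or stopping came later.

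The last row follows from the prohibition running to the end-of-study visit. Blood chemistry and central-laboratory biomarkers are scheduled at EOS, when there is no treatment left to discontinue.

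**Step 3. Size.** The plan gives no figure of its own. Inputs: about n = 20 evaluable per arm (protocol section 5); an assumed 30% relative fall in liver fat caused by the prohibited drug; k affected participants.

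- Responder proportion (SAP 6.2.2): 1/20 = 5 percentage points per participant.
- Shift in the arm's geometric-mean ratio: 1 − exp(k × ln(0.7)/20).
  - k = 1: ln(0.7) = −0.3567; −0.3567/20 = −0.0178; 1 − exp(−0.0178) = 1.8%.
  - k = 2: 1 − exp(−0.0357) = 3.5%.
- With half that effect (15%) and k = 1: ln(0.85)/20 = −0.0081; shift 0.8%.

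The 30% is an upper-end value. Protocol 4.1.3 associates falls of at least 30% with high-efficacy active treatment, and protocol 4.2 calls twelve weeks the shortest period for measurable change. A drug begun after Day 57 has at most 85 − 57 = 28 days before the Day 85 scan.

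**The case against.** The strongest reply is that mandatory discontinuation already does most of the work. This stands in large part. A reader might infer that the SAP simply keeps all efficacy data after these drugs; it does not. When the protocol is followed, ALT, ELF and other non-imaging values go from the discontinuation day.

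Other stronger readings also fail:

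- *The last month is unobserved.* Day 71 is a scheduled telephone visit with a medication review, so undetected use before Day 85 should usually last about 14 days. Table 8-1, as extracted, also appears to mark dosing on Day 85, with assessments before the dose. If so, use found at that visit could still trigger discontinuation and remove that day's ELF and ALT, though not the MRI.
- *The SAP removes the irrelevant and keeps the relevant.* COMD01 also covers antidiabetics, insulin, fibrates, statins, niacin and ezetimibe, while glucose, insulin, HOMA-IR, HbA1c and lipids are secondary endpoints.
- *All uncoded drugs act on the endpoints.* The documents support this for obeticholic acid (ALT) and make weight loss relevant. They state no endpoint effect for vitamin E. Its case rests on the prohibition and on its longer stability requirement, six months against three.
- *The bias favours the study drug.* Cohort 1 has two active arms and no placebo. A flattering bias is plausible within an arm or against historical placebo, but not predictable between arms.
- *The SAP's authors judged discontinuation insufficient.* No motive is stated. COMD01 may simply track the classes allowed on stable dosing.

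The general wording of the efficacy/PD set is a partial safeguard, but SAP section 6 sends deviation exclusions to Table 4-1, where these drugs do not appear.

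**Conclusion.** The gap is real but small. Four groups of drugs prohibited by protocol Table 6-2 have no deviation code, and discontinuation does not fully substitute for one. MRI from study day 56, values between drug start and discontinuation, and Day 85 or EOS values where use is found or begun after treatment is complete can all remain.

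The 1.8% shift for one participant (3.5% for two) assumes equal weighting of 20 participants and the upper-end effect; it falls to 0.8% for one participant at half that effect. The frequency of such use is not given in the documents and is assumed to be low. In a non-confirmatory study with safety as the primary objective, this is a worthwhile tidy-up and not a threat to the study's conclusions.

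**What to change.** Amend SAP Table 4-1 before database lock, a route the table's own closing note provides. Either extend COMD01 or add a parallel code so that starting obeticholic acid, a weight-loss drug, vitamin E at a dose Table 6-2 prohibits, or another investigational drug excludes efficacy/PD data from that drug's start day onwards. State that this includes imaging and takes precedence over the day-56 exception in SAP section 6.

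The cost is one table row and possibly a few more excluded values. The change concerns data handling only and leaves the protocol's treatment rules as they are.
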